#### **4.7. STATISTICAL ANALYSIS**

Data will be extracted from the centralized database for blinded analysis, based on intention to treat. The efficacy of randomization will be assessed by comparability and homogeneity of the intervention and control groups. Losses to follow-up will be calculated for each group and evaluated to determine whether the proportion of losses is independent of assignment to the intervention or control group.

Qualitative variables will be described as frequencies or percentages, and quantitative variables by the mean and standard deviation or interquartile range. Analysis will be stratified by study groups and compared at basal level using the  $\chi^2$  test for qualitative and the Student t or Mann-Whitney U test for quantitative variables.

Pulmonary function, anthropometric data, foods consumed, and MD adherence at V1 will be compared to values obtained at the final visit (V5). A multivariate analysis will be performed to determine the factors independently associated with the observed changes, adjusting for relevant covariates. The results will be presented as

hazard ratios, with 95% confidence intervals. All analysis will be performed with the SPSS v22.0 program, considering a p-value <0.05 statistically significant.

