## 1. SUMMARY

Recent studies have shown the impact of eating patterns on lung function. However, the specific benefits of the Mediterranean Diet (MD) in preventing pulmonary dysfunction are not well known.

**Objective.** To evaluate the effect of MD adherence on the deterioration of lung function in smokers.

**Methodology.** Design: Controlled, parallel, multicenter, cluster-randomized clinical trial. Participants: 750 active smokers aged 25 to 75 years with a cumulative consumption of more than 10 packets/year, without previous respiratory disease and who agree to the conditions of the study and sign an informed consent to participate. Scope: 20 Primary Care Centers managed by the Catalan Health Institutes in Tarragona Province, to be randomly assigned to a control or an intervention group (1:1). All participants will receive advice to quit smoking. Intervention: A 2-year nutritional intervention designed to increase MD adherence. Elements include: 1) annual visit to deliver personalized nutritional education, 2) annual telephone contact to reinforce the intervention, and 3) access to an ad hoc online dietary blog. Control group: Continuation of usual diet pattern. Assessment (both groups, initially and annually for two years): a) pulmonary function, evaluated by forced spirometry and b) adherence to the MD, evaluated by a 14-item questionnaire and medical tests. Statistical analysis: Intention-to-treat basis, with the individual smoker as unit of analysis. Pulmonary function and adherence to a Mediterranean-style diet in both groups will be compared.

**Expected results.** MD adherence prevents the deterioration of lung function in smokers without previous respiratory disease. Thus, MD is key to pulmonary disease prevention, together with the recommendation of smoking cessation.

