### **3. PROJECT DESCRIPTION**

#### **3.1. BACKGROUND OF THE TOPIC**

Nutrition and dietary habits are recognized factors in the development, progression, and prevention of chronic pathologies such as cancer and cardiovascular diseases [1,2]. However, the impact of diet on lung function and respiratory diseases is not as well established [3].

In our environment, smoking is the main factor in the etiopathogenesis of respiratory pathology, although other factors may also be involved, such as environmental agents, respiratory infections, genetic disorders, and dietary habits [4]. Inhalation of tobacco smoke particles accelerates the physiological decline of lung volume attributable to aging and increases susceptibility to respiratory dysfunction [5]. For years, it has been known that tobacco smoke generates thousands of free radical particles, an important source of oxidative stress and inflammation.

This effect can be neutralized by the action of enzymatic antioxidants such as superoxide dismutase, catalase, or glutathione peroxidase. Dietary intake of other antioxidants also may have a protective effect on lung function [6]. Specifically, evidence of the protective action of certain food and nutrients on pulmonary ventilation parameters such as forced vital capacity (FVC) and expiratory flow in the first second (FEV1) has been reported [7]. Thus, consumption of fruits and vegetables with a high content of antioxidant vitamins, phenolic compounds, minerals, and dietary fiber has a positive effect on respiratory health [8-9]. Omega-3 fatty acids present in blue fish and shellfish have beneficial effects on the inflammatory mechanisms involved in the pathophysiology of chronic obstructive pulmonary disease (COPD) [10]. In contrast, high consumption of processed meat has been associated with worse pulmonary function and increased risk of COPD [11-12]. Also, low or moderate alcohol consumption has been associated with better lung function, while excessive intake has detrimental effects [13-14].

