#### **3.3.3 Secondary objectives**

In smokers without previous respiratory disease:

- 1) To evaluate the effectiveness of a multicomponent nutritional educational intervention designed to increase adherence to the MD pattern.
- 2) To study the relationship between lung function and anthropometric parameters such as the abdominal circumference (AbC) and body mass index (BMI).
- 3) To study the relationship between lung function and various markers of food consumption, inflammation and oxidation.

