#### **4.6. STUDY VARIABLES**

A) The main variable of interest is impaired lung function at the end of follow-up, defined as at least one of the following values: FVC <80%, FEV1 <80%, and FEV1/FVC <0.7 [27]. As secondary variables, spirometry tests (FVC and FEV1), anthropometrics (BMI and AbC), and dietary patterns (adherence and diameter consumption markers) will be evaluated at the end of follow-up.

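### Section 4.7 spells out only a V1-to-V5 comparison for lung function, anthropometry, foods and diet adherence, which tests change over time and can be significant with no diet effect whenever both arms change

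*Combined protocol and SAP*

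**What the plan says.** Section 4.7 has three sentences that bear on this.

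- Baseline: "Analysis will be stratified by study groups and compared at basal level using" chi-square, Student t or Mann-Whitney tests. These are the only between-group tests it names for the study variables. Arm is mentioned otherwise only for losses to follow-up.
- Outcomes: "Pulmonary function, anthropometric data, foods consumed, and MD adherence at V1 will be compared to values obtained at the final visit (V5".
- Modelling: "A multivariate analysis will be performed to determine the factors independently associated with the observed changes, adjusting for relevant covariates". Results are to be given as hazard ratios.

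Other sections frame the trial as a comparison of arms. The Summary (section 1) states: "Pulmonary function and adherence to a Mediterranean-style diet in both groups will be compared". Secondary objective 1 (section 3.3.3) is: "To evaluate the effectiveness of a multicomponent nutritional educational intervention designed to increase adherence to the MD pattern". Section 4.3 sizes the trial on two group proportions, 0.17 and 0.31. Section 6 discusses whether the two study groups will differ. None of these places gives a test, model or effect measure for the arm contrast.

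**The concern.** The null hypothesis of a V1-to-V5 comparison is no change in 24 months. The null that matters is no difference between programme and control. The second does not imply the first. The background (section 3.1) says that smoking "accelerates the physiological decline of lung volume attributable to aging", so some fall in lung volume is expected in both arms whatever they eat. Both arms also have the same pattern of contacts and receive advice to stop smoking (section 4.4), either of which could move secondary variables in controls too.

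Two errors then become possible. A rise in adherence in the intervention arm could be credited to the programme although controls rose equally. In the other direction, a diet that truly slows decline could still leave a significant deterioration in the intervention arm. The multivariate sentence does not close the gap, because it looks for factors associated with change without making arm the tested term. Hazard ratios also do not suit a change in FEV1, BMI or a score between two fixed visits.

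**Working it through.** **The design is between arms.** The plan's own figure confirms this. With the arcsine formula, h = 2·asin(√0.31) − 2·asin(√0.17) = 0.331. Then n = 2·((1.96 + 0.842)/0.331)² ≈ 143.3, so 144 per group, and 144/0.75 = 192, as section 4.3 states. The contrast that was powered is one group against the other, not V1 against V5.

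**Inputs for the illustration**
- From the documents: 20 centres allocated 1:1, so 10 per arm; 38 participants per centre; 25% loss; design effect 1.7; two-sided α 0.05.
- Derived: completers per centre 38 × 0.75 = 28.5, taken as 28, so 280 per arm. ICC = (1.7 − 1)/(38 − 1) = 0.019.
- Assumed, because the documents give none: a shared FEV1 change of −40 or −80 mL with SD of change 200 or 300 mL; a shared rise of 0.25 points on the 14-item score with SD 2; and the same ICC for these continuous changes as for the binary main variable.

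**Formula, with one case by hand.** The individual-level within-arm test uses SE = SD/√280. With 28 per centre the variance of the mean is larger by 1 + 27 × 0.0189 = 1.51. For a 40 mL fall with SD 300, SE = 300/√280 = 17.9, and the true standard error is 17.9 × √1.51 = 22.0. The chance of rejection is about Φ((40 − 1.96 × 17.9)/22.0) = Φ(0.22) ≈ 0.59. With no change it is 2 × (1 − Φ(1.96/√1.51)) ≈ 0.11.

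**Simulated rejection rates with no diet effect**

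| Shared change (SD) | Within arm, individuals | Within arm, centre means | Between arms, centre means |
|---|---|---|---|
| None | about 11% | 5% | about 5% |
| FEV1 −80 mL (200) | 100% | about 100% | about 5% |
| FEV1 −80 mL (300) | 98% | 90% | about 5% |
| FEV1 −40 mL (200) | 87% | 68% | about 5% |
| FEV1 −40 mL (300) | 58–59% | 37% | about 5% |
| Score +0.25 (2) | about 55% | 33–34% | about 5% |

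The centre-level column separates the two problems. Ignoring centre inflates the milder cases, but the within-arm test still rejects far more than 5% of the time once clustering is allowed for.

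**Without clustering or a unit.** Using the normal approximation with 281 completers per arm (375 × 0.75), the within-arm rejection rate depends only on shared change divided by its SD: 5% at 0, 13% at 0.05, 39% at 0.10, 71% at 0.15 and 92% at 0.20.

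**Reading one arm against the other.** At +0.25 points, exactly one arm is significant in about 49% of trials with no diet effect, since 2 × 0.54 × 0.46 ≈ 0.50.

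**A true effect.** If the diet halves an 80 mL decline, the intervention arm falls by 40 mL. The individual-level test then reports significant deterioration in that arm in 58–87% of trials.

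**The case against.** The strongest reply is that this is loose drafting and not a wrong test. The analysis is by intention to treat and by study group, arm could naturally enter the multivariate model, and the Summary, sample size and limitations all presuppose a comparison of groups. That stands as to intent. A reader might infer that no arm comparison is planned, or that effectiveness will be judged from within-arm p-values. The documents say neither.

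The second reply is that significance without a diet effect is conditional, and this also stands. A reader might infer that the V1-to-V5 test will come out significant regardless. The documents do not support that. They give no expected change or SD for any variable, they support a shared decline for lung volume only, and controls are meant to keep their usual diet. With no shared change a test that allows for centre rejects 5% of the time. Even at a 40 mL fall with SD 300, both arms are significant in only about 34–36% of trials. If spirometry is analysed as percent of predicted, which the 80% thresholds in section 4.6 suggest but do not state, part of the ageing decline would be absorbed.

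What remains is that section 4.7, the operative section, does not turn the documented intent into a test of arm, and the comparison that it does state answers a different question.

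**Conclusion.** The point holds as a gap between design and analysis text. The only outcome comparison written out for lung function, anthropometry, foods and adherence is one of change over time. It does not estimate the effect of the programme, and it can be significant with no such effect whenever both arms change. The rates of 98–100%, 58–87% and about 55% (90–100%, 37–68% and about 34% on centre means) are illustrations resting on assumed changes, SDs and ICC; they do not predict what this trial will show. What does not depend on the size of the shared change is that it cancels in a between-arm comparison, which stays near 5% if centre is allowed for. The plan should be changed, but the data collection and design are not invalidated, because the intended comparison is clear from other sections.

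**What to change.** Replace the V1-to-V5 sentence in section 4.7. For FEV1, FVC, BMI, abdominal circumference, foods consumed and the 14-item adherence score, estimate the between-arm difference at V5, adjusted for that variable's baseline value, in a model that allows for centre. Test the arm term and report it with a 95% CI. Allowing for centre matters because the Summary takes the individual as the unit of analysis: an unadjusted between-arm test at a design effect of 1.7 would reject in 2 × (1 − Φ(1.96/√1.7)) ≈ 13% of null trials. Keep V1-to-V5 changes within each arm as description, and state that no conclusion on effectiveness will be drawn from them, or from one arm being significant and the other not.

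Two points must be settled first. Baseline spirometry is marked at V0 in the section 5 schedule, but section 4.5 lists it at V1 and section 4.7 uses V1; name the visit that supplies the baseline value. Abdominal circumference is a secondary variable in section 4.6 but is absent from the section 4.5 collection list; confirm that it is recorded.

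The cost is mainly wording, plus those two checks, with no extra participants or visits. The downside is that fewer results will be called significant, because change shared by both arms no longer counts.

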## **4. METHODOLOGY AND WORK PLAN**

### **4.1. DESIGN**

A multicenter, cluster-randomized, controlled clinical trial aimed at assessing the effect on lung function of increasing MD adherence in a cohort of smokers without previous respiratory pathology. (Clinical Trial registry with Nº 000).

Figure 1 shows the flow diagram of the project.

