### **4.3. CALCULATION OF THE SAMPLE**

The sample size was initially calculated for a simple randomized design, using the ARCSINUS approximation. Thus, in a bilateral contrast, accepting a risk  $\alpha = 0.05$ , a risk  $\beta < 0.2$  and a follow-up loss rate of 25%, 192 subjects are required in each group to detect significant differences between two proportions, estimating that this would be 0.17 in group-1 and 0.31 in group-2 [20]. Accepting that the effect of the design is 1.7, applying an intraconglomerate correlation coefficient  $< 0.05$  [23], a sample of 750 participants will be needed, 375 in each group (38 volunteers from each participating PCC).

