#### **4.4. INTERVENTIONS**

Participating centers will be assigned randomly to a control or intervention group (1:1). Volunteers will be referred to an initial visit (V0) to confirm inclusion criteria and sign an informed consent (Annex 1). Basal variables will be collected at that time.

Participants from the intervention PCCs will enter into an educational program to increase adherence to the MD. It will consist of five contacts that integrate three operational components:

- a) Explain the details of the MD and the benefits of following this dietary pattern in an individual visit of 25-30 minutes (V1). Data on the study variables will be collected and medical tests will be performed. This data gathering will be repeated annually for two years (V3 and V5).
- b) Clarify any doubts about following the MD pattern and other advice received, in a telephone conversation. This annual contact will reinforce the intervention (V2 and V4).
- c) Provide information about MD foods, cooking tips, adapted recipes, and other related topics in an ad hoc nutrition blog.

The control group will carry out the same 5 visits (3 individual visits and 2 phone calls), although no changes will be made in their usual diet and they will not be provided with access to the nutritional blog.

All participants will receive health advice to stop smoking, according to the protocol recommended to health professionals in Catalonia: a proposal of smoking cessation expressed in a clear, firm, and personalized way, in an empathic and respectful setting.

At the end of the study, if the intervention is effective, control group members will be invited to participate in the same intervention program.

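### Centres are randomised, but the plan analyses individual smokers and names no method that accounts for centre; unadjusted, a nominal 5% test has a real error of about 11–13% under the plan's own clustering assumption.

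*Combined protocol and SAP*

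**What the plan says.** Section 4.1 describes "A multicenter, cluster-randomized, controlled clinical trial", and section 4.4 allocates the centres 1:1. Section 4.2 gives 20 centres.

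Section 4.3 allows for clustering in the sample size: "Accepting that the effect of the design is 1.7, applying an intraconglomerate correlation coefficient" below 0.05. It arrives at 750 participants, about 38 per centre.

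The Summary states the analysis as "Intention-to-treat basis, with the individual smoker as unit of analysis".

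Section 4.7 is the only analysis section. It names the chi-square, Student t and Mann-Whitney tests for the baseline comparison only: "Analysis will be stratified by study groups and compared at basal level using the" chi-square and other tests. For outcomes it compares V1 with V5 values and then says: "A multivariate analysis will be performed to determine the factors independently associated with the observed changes, adjusting for relevant covariates". Results are to be given as "hazard ratios, with 95% confidence intervals".

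Section 4.6 defines the primary endpoint: "The main variable of interest is impaired lung function at the end of follow-up, defined as at least one of the following values". It is a yes/no status at one time point.

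**The concern.** Smokers from one centre share staff, training, equipment and catchment area, so their outcomes are correlated. The plan expects this, since it enlarges the sample for it. Enlarging the sample protects power, but it does nothing to the standard error of the test that is later run. That standard error is right only if the analysis itself accounts for centre.

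An individual-level analysis is legitimate when the model carries the clustering. The plan fixes the individual as the unit and does not say that the model will do so. Adjustment for covariates does not close the gap. A full set of fixed centre terms is collinear with arm, because each centre is wholly in one arm. Individual covariates remove only the between-centre variation that they happen to explain.

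At stake is the primary conclusion: p-values would be too small and intervals too narrow.

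The effect measure is a second, separable sign that the outcome model was not matched to the design. A hazard ratio needs time to event, and the endpoint is a status at the end of follow-up.

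**Working it through.** **Inputs from the plan.** 20 centres (4.2), allocated 1:1 (4.4), so 10 per arm. Two-sided α 0.05, power 80%, proportions 0.17 and 0.31, loss 25%, design effect (DE) 1.7, intracluster correlation (ICC) below 0.05, N = 750 (all 4.3).

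**Assumptions.** Equal cluster sizes and the same ICC in both arms. All error figures are conditional on an outcome analysis that ignores centre.

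**Step 1. Reproduce the plan's figure.** With the arcsine formula, h = 2·asin(√0.31) − 2·asin(√0.17) = 0.331. Then n = 2·((1.960 + 0.842)/0.331)² = 143.3, rounded up to 144, and 144/0.75 = 192 per group. This matches section 4.3.

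The next step in 4.3 does not reproduce: 192 × 1.7 = 326 per group, not 375. The ratio 375/192 is 1.95.

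**Step 2. ICC implied by the design effect.** DE = 1 + (m − 1)·ICC. With m = 750/20 = 37.5, ICC = 0.7/36.5 = 0.0192.

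**Step 3. Cluster size at analysis.** 750 × 0.75/20 = 28.1 completers per centre. At ICC 0.0192, DE = 1 + 27.1 × 0.0192 = 1.52.

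**Step 4. Real error when centre is ignored.** Error = 2·(1 − Φ(1.96/√DE)).

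| Setting | DE | Real error |
|---|---|---|
| DE as stated | 1.70 | 13.3% |
| ICC 0.0192, 28.1 per centre | 1.52 | 11.2% |
| ICC 0.005, 28.1 per centre | 1.14 | 6.6% |
| ICC 0.0096 (half the between-centre variance explained) | 1.26 | 8.1% |
| ICC 0.01, 28.1 per centre | 1.27 | 8.2% |
| ICC 0.05 (the plan's upper bound), 28.1 per centre | 2.36 | 20.2% |

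For the first two rows, 1.96/√1.70 = 1.503 and 1.96/√1.52 = 1.590. Valid intervals would be √1.70 = 1.30 and √1.52 = 1.23 times as wide on normal quantiles. On 18 df (t = 2.101) the factors are 1.40 and 1.32.

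**Step 5. Check by simulation.**
- *Two-proportion z test ignoring centre* (beta-binomial outcomes, 10 + 10 centres, 200,000 runs): 13.3–13.4% with 38 per centre and 11.2% with 28 per centre at the implied ICC; about 20% at ICC 0.05 with 28 per centre.
- *Logistic model with arm and two individual covariates but no centre* (covariate effects assumed at 0.5 and 0.3 log-odds per SD, 8,000 runs): 11.3% at ICC 0.0192 and 14.1% at ICC 0.026. The latter ICC gives DE 1.7 with 28 per centre.
- *t test on centre proportions, 18 df*: 4.9–5.2% in all settings.

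**Step 6. Power of a valid analysis.** Effective number per arm = 281.25/DE, for 0.17 vs 0.31.

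| Setting | 18 df | Normal |
|---|---|---|
| ICC 0.0192 (DE 1.52) | 86% | 89% |
| DE 1.7 | 82% | 86% |
| ICC 0.05 (DE 2.36) | 68% | 73% |

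Power falls below 80% above an ICC of about 0.028 (18 df) or 0.036 (normal).

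**The case against.** The strongest reply is that the plan is silent rather than wrong. An individual unit of analysis is compatible with a mixed model or GEE, the authors plainly know about clustering, and the analyst may intend such a model. This is fair, and it is why every error figure is conditional. It does not close the gap: no section commits to any method that accounts for centre, so an ordinary regression would comply with the plan as written.

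Other points that stand in part:

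- **The range 11–13% joins two settings.** 13.3% belongs to DE 1.7 as stated. 11.2% belongs to DE 1.52 after the planned loss.
- **The plan's DE is not firm.** The final N implies a factor of 1.95, at which the error would be 16.1%, and the ICC is given only as an upper bound.
- **The tests evaluated are stand-ins.** Section 4.7 names no between-arm test of the primary endpoint. The inflation comes from the ignored correlation, and the z test and the logistic model gave similar results.
- **Covariates that differ between centres would reduce the inflation.** If they explained half the between-centre variance, the error would be about 8.1%, still above 5%. The covariate-adjusted simulation does not assess this benefit, because its centre effects were generated separately from the covariates.
- **Hazard ratios are a separate matter.** Clustered survival models exist. The mismatch is with the binary endpoint, not with clustering as such.

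**Conclusion.** The concern holds and must be fixed before analysis. The design is clustered, the sample size treats it as clustered, and the stated analysis does not. Without adjustment for centre, the nominal 5% test runs at 13.3% at the stated design effect, or 11.2% once the planned loss shrinks the clusters. The range over plausible ICCs is 6.6% to 20.2%.

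These figures rest on 10 centres per arm, equal cluster sizes and a common ICC. Unequal recruitment across centres was not evaluated; it would generally raise the design effect. The direction of the error does not depend on the exact ICC: any positive within-centre correlation left out of the model makes the test too liberal. The hazard-ratio mismatch is a valid but secondary point.

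**What to change.** In section 4.7, name one cluster-appropriate primary analysis of the binary endpoint. Any of these would do:

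- a mixed logistic model with a random centre intercept, with a small-sample correction for 20 clusters;
- GEE clustered on centre, with a small-sample correction;
- a comparison of centre-level proportions, covariate-adjusted if wished, on 18 df.

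Apply the same principle to the secondary outcomes, list the covariates in advance, and report the estimated ICC. Replace hazard ratios with the measure that the chosen model gives: odds ratio, risk ratio or risk difference. In the Summary, describe an individual-level analysis that accounts for clustering by centre, or a centre-level analysis if that is chosen.

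The cost is wording, a slightly more complex model and honest, wider intervals. At the plan's own clustering figures the planned 80% power is kept without more participants. That margin is lost if the true ICC approaches 0.05, so section 4.3 should state a point value for the ICC and show how 750 was reached.

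### Section 4.7 names hazard ratios as its only effect measure, but the primary endpoint is yes/no impairment at the end of follow-up and the trial is sized on two proportions

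*Combined protocol and SAP*

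**What the plan says.** Four places in the combined protocol and SAP bear on this point.

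- **4.6 Study variables.** "The main variable of interest is impaired lung function at the end of follow-up". It is met by any one of three spirometric thresholds, so each participant is impaired or not at one visit. Spirometric values, anthropometry and diet are secondary.
- **4.3 Calculation of the sample.** The trial is sized to "detect significant differences between two proportions", 0.17 and 0.31, two-sided at 0.05.
- **4.7 Statistical analysis.** The tests it names (chi-square, Student t, Mann-Whitney) belong to a baseline comparison: "Analysis will be stratified by study groups and compared at basal level". For outcomes, it sets V1 values of lung function, anthropometry, food intake and diet adherence against those at V5. It then plans an unnamed multivariate analysis "to determine the factors independently associated with the observed changes", with results given as "hazard ratios, with 95% confidence intervals".
- **1 Summary.** "Pulmonary function and adherence to a Mediterranean-style diet in both groups will be compared", by intention to treat and "with the individual smoker as unit of analysis". No measure or model is given.

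**The concern.** A hazard ratio compares rates of an event over time. It needs a defined event, a population at risk, event times, a censoring rule and a model. The plan supplies none of these for lung function; it defines a status at a fixed visit. The measure therefore fits neither the primary endpoint nor the sizing. It also cannot express changes in FEV1, FVC, BMI, abdominal circumference or the adherence score.

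At stake is prespecification of the main result. As written, the team would either report it on a scale that the endpoint and sizing do not use, or choose the scale and model once the data are in hand.

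**Working it through.** **Step 1. Reproduce the sizing, to see which scale it uses.** Inputs from 4.3: 0.17 and 0.31, two-sided alpha 0.05, power 80%, 25% losses, arcsine method.

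- h = 2·asin(√0.31) - 2·asin(√0.17) = 0.331
- n = 2·((1.960 + 0.842)/h)² = 143.3, rounded up to 144 evaluable per group
- 144/(1 - 0.25) = 192 per group, exactly the stated figure

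This is a pure two-proportion calculation. No hazard, event target or accrual assumption enters it, and naming a binary effect measure leaves the 192 unchanged.

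**Step 2. Planned effect on scales that fit a fixed-time yes/no endpoint.** Assumption: group-1 (0.17) is the intervention group; 4.3 does not say.

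- Risk difference = 0.17 - 0.31 = -0.14
- Risk ratio = 0.17/0.31 = 0.548
- Odds ratio = (0.17/0.83)/(0.31/0.69) = 0.456

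**Step 3. The hazard ratio implied by the same proportions.** This needs assumptions that are not in the plan, including that everyone is unimpaired at entry.

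- Constant hazards: ln(0.83)/ln(0.69) = 0.502
- Cox model, all events at one common time: 0.548 with Breslow ties, 0.504 with Efron ties
- Cox model, events at 12 and 24 months with equal yearly hazard: 0.525 (Breslow), 0.503 (Efron)

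The range of 0.50 to 0.55 is illustrative only. Section 4.2 excludes a history of respiratory disease but sets no spirometric limit at entry, so some participants may already meet the 4.6 definition.

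**Step 4. Expected precision on the sizing scale.** Inputs from 4.3: 375 per group, 25% losses, design effect 1.7. Evaluable n = 375 × 0.75 = 281.25 per group.

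- SE(RD) = √(1.7 × (0.17×0.83 + 0.31×0.69)/281.25) = √(1.7 × 0.355/281.25) = 0.0463; 95% CI -0.231 to -0.049
- SE(log RR) = √(1.7 × (0.83/(281.25×0.17) + 0.69/(281.25×0.31))) = 0.207; 95% CI 0.37 to 0.82

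**Step 5. Two readings of the sentence in 4.7.**

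- *It covers the group comparison.* Then the measure does not match 4.6 or 4.3.
- *It covers only the factors associated with change.* Then the randomised V5 comparison has no measure or model. The named tests are for baseline, the outcome comparison spelled out is V1 against V5, and the Summary says only that groups will be compared.

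The gap remains under both.

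**The case against.** The strongest defence has three parts.

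- **The sentence belongs to the factor analysis.** The preceding sentence supports this reading. Sections 4.3, 4.6 and the Summary together then identify the intended contrast: a two-sided comparison of two proportions impaired at the end of follow-up, by intention to treat. This stands in part. The contrast can be inferred, but its reporting measure and model still cannot.
- **A time-to-event analysis is feasible.** The schedule in section 5 gives a Day 0 and spirometry at 12 and 24 months, so a discrete-time model could be built. That is true, and a reader should not infer that a hazard ratio could not be computed. But the plan defines no such outcome, and 4.6 asks for status at the end.
- **It is a slip for odds ratio.** Possibly, since 3.2 reports odds ratios for the earlier observational study. Nothing in 4.7 says so.

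Two stronger arguments are tempting and should not be made.

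- A reader might infer that the harm lies in taking a hazard ratio for a risk ratio: a 50% relative reduction (1 - 0.502) instead of 45% (1 - 0.548). An odds ratio, which is an ordinary choice here, would mislead more if misread (1 - 0.456 = 54%), so misreading is not the ground for the point.
- A reader might infer that a hazard ratio costs precision. With 281.25 per group and before clustering, a Breslow fit at one common time has a model-based standard error of 0.180 on the log scale, against 0.159 for the risk ratio. With a robust variance the Cox standard error is also 0.159. A naive variance would be wrong for any measure when centres are randomised.

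**Conclusion.** The point holds. The only effect measure in 4.7 does not fit the primary endpoint, the sizing or the continuous changes it is attached to, and no other text gives the randomised V5 comparison a measure or model.

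The consequence is limited to prespecification and scale. The planned contrast is a risk difference of -14 points (95% CI -23 to -5) or a risk ratio of 0.55 (0.37 to 0.82), assuming the rates, losses and design effect in 4.3 and that group-1 is the intervention. The corresponding hazard ratio cannot be fixed from the documents.

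A reader might go further and infer that the trial is wrongly sized or underpowered for this reason. The documents do not support that: the two-proportion figure of 192 reproduces exactly and does not depend on how the result is reported. Nor do they show that the team intends a Cox model, since none is named.

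**What to change.** In 4.7, replace the whole sentence that ends with "hazard ratios, with 95% confidence intervals" by:

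> The primary result is the comparison of impaired lung function at V5 between intervention and control, reported as a risk difference and risk ratio with 95% CI, from a binary-outcome GEE (identity and log link) with study group as the main term, adjusted for baseline impairment, clustered by centre, with robust standard errors and a small-sample correction for 20 centres. FEV1, FVC, BMI, AbC and adherence score are reported as between-group mean differences at V5, adjusted for the baseline value, with 95% CI from a centre-clustered linear model. The exploratory factor analysis is reported as risk ratios for impairment and as mean differences for continuous changes.

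If time to impairment is also wanted, make it a separate secondary endpoint with its own event, origin, risk set and handling of interval censoring between annual spirometries.

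Two practical checks go with the new text. Confirm that SPSS v22.0 can fit these models with the small-sample correction, and name a fallback in case a link does not converge. State which visit supplies baseline spirometry, since the schedule table in section 5 places it at V0 and 4.7 uses V1.

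Cost: a few sentences in 4.7 and slightly more analysis work. No new data and no change in sample size.
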